Phone conversations will be limited to providing information about the study and to pre-screening questions. If potential subjects are more comfortable answering questions in person, they will be invited to come in for the screening. At the screening visit, informed consent and details of the study will be discussed in a private room in the Berenson-Allen Center to encourage free exchange of information and only questions pertinent to study participation will be asked.

Physical Setting

Recruitment and screening procedures will take place by study staff at the Beth Israel Deaconess Medical Center. Data will be stored at BIDMC and data analysis will occur at BIDMC or Boston University. In the event that some specialized processing algorithms are run on computers outside BIDMC only de-identified data will be transmitted. MRI scanning will take place at Boston University Cognitive Neuroimaging Center under a separate protocol. All TI stimulation experimental sessions will take place in the Berenson-Allen Center at BIDMC.

B8. DATA SECURITY

All data will be de-identified with the use of unique subject identifiers per HIPAA guidelines. Names will not be provided to external sources, nor will any identifying marker be published in which a participant could be distinguished. All paper records regarding this research project will be stored in the locked offices of the research study team, located within the BA-CNBS at BIDMC. De-identified data will be stored on computers protected by individual user passwords to restrict access, using available secure data basing suites of REDCap and XNAT when possible. The XNAT will be hosted and managed by BIDMC and will be kept behind the firewall for security purposes.

MRI scan images will be sent to BIDMC from BU using a secure file transfer. Any paper forms from BU (e.g. adverse event forms) will be scanned and sent to BIDMC via encrypted email. Medical records from outside providers will be requested and obtained via secure email or fax.

Information that will be shared with BU for the MRI study will include PHI that is required to contact the participant for scheduling. All information will be provided via secured email and/or secure file transfer.

Data will be shared with McLean Hospital. As a co-investigator and collaborator at McLean Hospital, [name] will be on BIDMC premises during study visits to help collect data and will have inperson access to the participants. He will have all data collected by the BIDMC research staff. This data includes PHI.

De-identified data will be sent to the National Institute of Mental Health Data Archive (NDA). All data will be labeled with a Global Unique Identifier (GUID) that is obtained through a system provided by the NDA. Participants will have the option of opting in or out of having their data shared with the NDA.

B9 Multi-Site Studies

Is the BIDMC the coordinating site? \Box Yes \Box No

Is the BIDMC PI the lead	investigator of the multi-site study?	🖂 Yes	□ No

Research teams from both locations will communicate via phone, email or conference calls on a monthly basis or more, as needed. In these interactions, teams will assess safety and review study progress.

Adverse events that occur at BU will be communicated to BIDMC study staff for completion of DSMB, and IRB communication as described above in the "Data Safety Monitoring Plan".

All data analysis will be managed by BIDMC although MRI and visual discrimination analysis will be completed in a collaborative manner between the sites. Regular meetings will be scheduled as described above with ad hoc meetings scheduled as needed. BIDMC will manage protocol amendments that affect the overall study aims. Recommended changes that affect the MRI imaging protocol will be communicated to the BU study team either in the monthly meeting or via phone and/or email in real time. Any amendment needs that are identified by the BU team for the MRI imaging protocol will be communicated to the BIDMC team in the same manner.

Data will be shared with a collaborator at Hebrew Senior Life, specifically, [name]. De-identified MRI data will be shared with a collaborator at Northeastern University, specifically, [name]. Any data that is sent to HSL and Northeastern University will be deidentified and sent via encrypted procedures per BIDMC policy.

B10 Dissemination of Research Results

We will send a follow-up e-mail thanking subjects for their participation in the study. In this follow-up e-mail, we will inform subjects that results of the study will be available on our website tmslab.org as all publications are available on the website.

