NCT Number:	NCT03747601
Official Title:	Temporal Interference Brain Stimulation (TI)
Document Type:	Protocol with Qualitative Analysis Plan
Document Date:	09/01/2020

PART B STUDY DESCRIPTION

	The Development and Human Translation of Temporal Interference Brain Stimulation
Principal Investigator	[name]

B1. PURPOSE OF PROTOCOL

The primary aim of this study is to translate temporal interference (TI) stimulation methodology into humans and examine its safety, feasibility, steerability, and focality. In the proposed early phase human experiment, we will assess the ability to apply TI stimulation along spatial dimensions to selectively modulate neural activity and assess the feasibility of selective targeting deep brain structures without exciting overlaying cortex. The overall goal of the study is to advance TI methodology and its translation to humans.

The specific aims in this study are to

- Assess the safety of TI stimulation.
- Assess the feasibility, focality, and steerability of TI stimulation by selectively modulating activity in subregions of a cortical area (calcarine cortex)

We hypothesize that TI stimulation can be used to impact different regions of the visual field that are represented within the calcarine fissure of the human brain.

We hypothesize that TI stimulation is possible in regions within the calcarine fissure without impacting intervening regions.

We hypothesize that TI will be well tolerated by human subjects and side effects will be consistent with other forms of transcranial electric current stimulation (tES).

B2. SIGNIFICANCE AND BACKGROUND FOR THE STUDY

Current brain stimulation methods have limitations:

[figure not shown]
Deep brain stimulation (DBS) has had great impact in disorders such as Parkinson's disease and obsessive-compulsive disorder and has potential for other disorders such as depression and Alzheimer's disease. DBS works by delivering focal electrical stimulation from electrodes surgically implanted in deep, often sub-cortical regions. Being a surgical procedure, it bears the potential for serious complications that limit adoption and scalability.

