Each subject will then undergo up to 4 TI stimulation sessions (2 minimum) separated by at least 2 days to minimize the risk of carry over effects of the stimulation. In each visit, the participant will receive TI stimulation to a region of retinotopic representation in the calcarine fissure. The cortical targets will be defined by electrical field modelling that will be used to optimize the electrode placement.

Stimulation visits will consist of TI stimulation combined with a visual discrimination task, with any changes in visual perception assessed by collecting behavioural responses (i.e. button presses) from the subject in response to visual stimuli presented before, during, and after TI stimulation.

Each visit will consist of up to four, 10 minute blocks of stimulation paired with a visual discrimination task. The stimulation blocks will be completed with TI stimulation at a difference frequency ranging from 1 to 80Hz, transcranial alternative current stimulation (tACS) stimulation with no temporal interference at a frequency ranging from 1 – 80HZ, or a no offset stimulation (e.g. matched carrier stimulation frequencies such that no envelope modulation is anticipated). The most common signal from visual cortex during wakeful relaxation is in the α frequency range (8-12 Hz). Due to this feature of visual cortex, we hypothesize that stimulation frequencies in and around α are likely to demonstrate TI efficacy. Moreover, since visual perception changes have been induced with tACS at 60Hz, we hypothesize that stimulation in and around this frequency will associate with detectable visual perception changes. We hypothesize that TI with a residual effective stimulation frequency of 1-80 Hz will be ideally suited for activation of the targeted visual cortex.

Each block will go as follows:

- 1. Baseline visual discrimination task to assess threshold
- 2. TI stimulation paired with the visual discrimination task and visual disturbance assessment (10 minutes)
- 3. Repeat visual discrimination task

Participants will have a 5 minute break between blocks.

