Participants will be monitored throughout the visit for any adverse effects and a tES side-effect questionnaire will be administered at the beginning and end of each stimulation visit to additionally track any adverse effects. Although any visual disruption induced by the stimulation is expected and anticipated to be transient in nature, at the conclusion of each visit, a standard automated visual perimetry assessment will be completed on a Humphrey Visual Field analyser to compare to baseline. If there is a change in the perimetry assessment, a study MD will evaluate the participant to determine the need for additional follow-up. If there are any immediate concerns, the participant will be further evaluated by the study ophthalmologist. Overall, each stimulation visit will take approximately 3 hours to complete.

Detailed Methods and Procedures:

Mini International Neuropsychiatric Interview (MINI):

All subjects will be screened as overseen by a board-certified psychiatrist using the Mini International Neuropsychiatric Interview, ver. 6.0 (MINI) to identify prospective subjects with exclusion criteria related to mental health.

If a subject answers affirmatively to the question "Did you repeatedly consider hurting yourself, feel suicidal, or wish that you were dead? Did you attempt suicide or plan a suicide?" within the past 2 weeks, a study MD (psychiatrist or neurologist) will be notified and will assess the participant/the participant's

responses. The MD may recommend follow-up with their primary care provider and/or with a mental health care provider. Although not anticipated in this study of healthy individuals, if a participant is thought to need urgent care, the participant's healthcare provider may be contacted by one of the study clinicians to develop a plan for follow-up. If there is concern for their immediate safety, they will be sent to the emergency room at BIDMC.

MRI

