Safety information will be tabulated as frequency of expected events (e.g. headache), and non-conforming safety information will similarly be tabulated and reported.

C. Subject Selection

The population of the Greater Boston area is 84% Caucasian, 9% African-American, 5% Hispanic and 2% Asian, with relatively similar numbers of men and women. Participants of any gender, race, ethnicity, religion, and sexual orientation will be included. All efforts will be made to include equal numbers of both genders and to include minorities in the studies in equal proportions to the Boston area.

Inclusion Criteria:

- Normal healthy volunteer
- 18-45 years of age
- Normal or corrected-to-normal vision
- Right handed

Exclusion Criteria:

- Visual impairment that may interfere with eye tracking equipment (for example glasses with high reflection)
- Any current or past history of a psychiatric disorder
- Any current or past history of neurological disorders or acquired neurological disease (e.g. stroke, traumatic brain injury), including intracranial lesions
- History of head trauma resulting in prolonged loss of consciousness; or a history of >3 grade I concussions
- Current history of poorly controlled headaches including intractable or poorly controlled migraines
- Any systemic illness or unstable medical condition that may cause a medical emergency in case of a provoked seizure (cardiac malformation, cardiac dysrhythmia, asthma, etc.)
- History of fainting spells of unknown or undetermined etiology that might constitute seizures
- History of seizures, diagnosis of epilepsy, history of abnormal (epileptiform) EEG, or family history of treatment resistant epilepsy with the exception of a single seizure of benign etiology (e.g. febrile seizures) in the judgment of a board-certified neurologist
- Possible pregnancy. All female participants of child bearing age are required to have a pregnancy test
- Any metal in the brain, skull or elsewhere unless approved by the responsible MD
- Any medical devices (i.e. cardiac pacemaker, deep brain stimulator, medication infusion pump, cochlear implant, vagal nerve stimulator) unless otherwise approved by the responsible MD
- Substance abuse or dependence within the past six months
- Pregnancy; all female participants of child bearing age will be required to have a pregnancy test; any participant who is pregnant will not be enrolled in the study.

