Adverse effects will be collected from the start of the experimental protocol to the end of study participation. All adverse events, regardless of attribution to TI or pre/post assessments, will be collected and recorded using a standard adverse event form. Participants will be asked, in an openended way, about the presence of any such events on a daily basis. Additionally, a standard questionnaire for tES-related adverse effects will be completed in the period after every TI session. Intensity of each adverse event will be graded as mild, moderate or severe. If an event occurs that is not expected (e.g. is not described in the research protocol or consent form), that indicates a change from baseline in cognition, and/or requires immediate attention, such as a seizure, the PI (or covering investigator) will be informed in real time to assess the event, advise on immediate care of the participant and to determine the necessary reporting steps. Any events that are serious or unexpected in nature, severity or frequency as compared to the risks described in the study plan will be reviewed by the principal investigator or designee (e.g. a co-investigator) to determine the relationship of the event to the study. Reportable events will be submitted to the IRB per determined policies and will be reported to the DSMB as described below.

Adverse Event Communication with Boston University for the MRI protocol

Adverse events related to the MRI imaging protocol at BU will be monitored and collected by study staff at BU. Following the completion of each subject, the staff at BU will share adverse events that were captured by their study team with the BIDMC study team. This information will be included in the summaries provided to the DSMB. A serious or unexpected adverse event that requires reporting to the BU IRB per the BU PI will be reported to the BIDMC study staff in parallel with the BU reporting procedures. These events will be shared with the DSMB in real time as will any local reportable events.

DSMB

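### In visits that mix TI with tACS or no-offset blocks, visit-level side-effect forms and a safety table without condition give, at best, an upper bound on the TI rate

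*Combined protocol and SAP*

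**What the plan says.** Safety is the first specific aim in B1: "Assess the safety of TI stimulation". The matching hypothesis has two parts: TI will be well tolerated, and "side effects will be consistent with other forms of transcranial electric current stimulation (tES").

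On visit content, B3.A (TI Sessions) states: "Each visit will consist of up to four, 10 minute blocks of stimulation paired with a visual discrimination task". A block may be TI, "transcranial alternative current stimulation (tACS) stimulation with no temporal interference at a frequency ranging from" 1 to 80 Hz, or stimulation with no frequency offset. The same section says that TI is given in each visit. The number and order of conditions within a visit are not stated. Two other places point towards separate visits: B2 (TI Validation with Visual Field Stimulation) mentions additional control sessions, and the General Safety Plan refers to tACS and TI visits.

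On collection, B3.A says that "a tES side-effect questionnaire will be administered at the beginning and end of each stimulation visit". Adverse Event Monitoring says that "a standard questionnaire for tES-related adverse effects will be completed in the period after every TI session". Neither places the form after a block. Subjects are also monitored throughout the visit, each block includes a visual disturbance assessment, and all adverse events go on a standard form.

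On analysis, B3.B says: "Safety information will be tabulated as frequency of expected events (e.g. headache"), with other safety information tabulated in the same way. Condition is not a factor in the table.

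**The concern.** If one visit holds both TI and tACS blocks, a sensation reported on the end-of-visit form cannot be assigned to either from that form, and the planned table does not try to assign it.

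The two parts of the hypothesis are affected differently. A low visit-level rate still supports good tolerability, because everything given in the visit was tolerated. The claim of consistency with other tES is more exposed. B5 counts tACS as a form of tES, so a tACS block can supply the expected profile whatever TI does. A TI rate near zero, which would favour the method, could be hidden in the same way.

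Timing matters too. B5 says that electrode sensations usually fade soon after stimulation starts, though some last longer. An end-of-visit form therefore relies on memory of earlier blocks. If condition at onset is not written down at the time, it may not be recoverable later.

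**Working it through.** The plan gives no safety rate, margin or power figure to reproduce. The figures below are illustrations.

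**Inputs from the protocol**
- At least 12 completers (B3.B).
- 2 to 4 TI visits, up to four 10-minute blocks per visit, 5-minute breaks (B3.A).
- General tES rates: tingling 20–70%, headache 10–15% (B5).

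**Assumptions:** B5 rates applied to one tACS block; other rates and recall levels chosen for illustration.

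**1. Forms against blocks.** End-of-visit forms: 12 × 2 = 24 to 12 × 4 = 48. With four blocks per visit they cover 24 × 4 = 96 to 48 × 4 = 192 blocks.

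**2. What a mixed visit shows.** Take one TI block (rate t) and one tACS block (rate p). The visit rate is max(t, p) if the same subjects react to both, and 1 − (1 − t)(1 − p) if reactions are independent.

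| Effect | p | t = 0 | t = p, full overlap | t = p, independent |
|---|---|---|---|---|
| Tingling, low end | 20% | 20% | 20% | 1 − 0.8² = 36% |
| Headache, low end | 10% | 10% | 10% | 1 − 0.9² = 19% |

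A visit rate of 20% therefore fits both a TI rate of 0 and a TI rate of 20%. Even under independence the tingling difference is 12 × (0.36 − 0.20) = 1.9 subjects.

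**3. When the upper bound fails.** Let t = 15% and the control rate be 5%, independent. The true visit rate is 1 − 0.85 × 0.95 = 19.25%. With 75% recall, the recorded rate is 0.75 × 19.25% = 14.4%, below the true TI rate of 15%. In this example the bound holds only if recall is at least 0.15/0.1925 = 78%. In a four-block visit, at least 3 × 5 + 3 × 10 = 45 minutes separate the end of block 1 from the end of block 4, before counting the discrimination tasks.

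**4. Unequal exposure.** Suppose 10% per block for every condition, with independent blocks. A subject with eight TI blocks has an event with probability 1 − 0.9⁸ = 57%; a subject with two tACS blocks, 1 − 0.9² = 19%. A by-condition table that counts only subjects would show a TI excess where none exists.

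**5. Precision with perfect attribution.** For 0/12, the exact two-sided 95% upper limit is 1 − 0.025^(1/12) = 26.5%. The probability of 0/12 is 0.8¹² = 6.9% at a true rate of 20%, 0.85¹² = 14.2% at 15%, and 0.9¹² = 28.2% at 10%.

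**The case against.** The strongest reply is that the questionnaire is only one source. Subjects are watched throughout the visit, and a sensation that fades soon after onset occurs in a known block while someone is observing. The fields of the adverse event form are not in the documents; if it holds an onset time, condition could be read from the session log. The pilot in B2 ran six block types and reported symptoms for TI separately, so this reporting is not foreign to the team. The hypothesis has no margin or test. With complete reporting, pooling makes TI look worse rather than safer. An effect unlike tES would still appear in the pooled table, and unexpected events that need immediate attention reach the investigator in real time.

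Much of this stands. Monitoring and the adverse event form may recover some attribution, and tolerability remains reportable. Overlap across the whole 20–70% tingling range would also be poor evidence, because it comes largely from the width of that range; the working therefore fixes a single rate.

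Three things remain. No section requires block or condition at onset. Relationship is reviewed only for serious or unexpected events, and to the study rather than to a condition. The one block-level item concerns visual disturbance and does not cover tingling, burning or headache.

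**Conclusion.** The point holds for mixed visits. There, the visit-level rate is at best an upper bound on the TI rate for the TI blocks given, and only with complete recall. It can support good tolerability but is a weak basis for consistency with other tES. At an assumed 20% tACS tingling rate, a visit shows 20% even when TI causes none.

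Three stronger readings are tempting and unsupported:
- **Every visit is mixed.** B3.A puts TI in each visit and permits control blocks, but does not mandate them. B2 and the General Safety Plan allow for separate control visits, and the TI Stimulation section uses TI loosely for some controls. Single-condition visits lose no attribution.
- **The visit-level rate is a firm upper bound.** Incomplete recall can put it below the true TI rate, as the 14.4% against 15% example shows.
- **The safety aim fails.** Whole-visit tolerability survives, and other records may help.

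The change is worth making because the stated start-and-end schedule loses information on the first specific aim at a point where keeping it is cheap. With about 12 subjects, better attribution gives a clearer description, not a test.

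**What to change.** 1. **B3.A, TI Sessions:** state whether conditions are mixed within visits and how block order is set. Reconcile this with the control sessions in B2 and the tACS and TI visits in the General Safety Plan.
2. **Questionnaire and adverse event form:** record block number and condition at onset. This is the minimum.
3. **B3.A, questionnaire schedule:** in mixed visits, give the short questionnaire at visit start and after each block, using the breaks already planned ("Participants will have a 5 minute break between blocks"). The form after the last block is the existing end-of-visit form.
4. **B3.B, safety analysis:** tabulate descriptively by condition at onset, both as blocks with an event over blocks delivered and as subjects with at least one event over subjects exposed. Show blocks per subject and condition, and block order. Give exact 95% CIs for the subject-level proportions only, and make no formal TI-versus-tACS test.

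If every visit is stated to hold one condition, item 3 is not needed and items 2 and 4 reduce to labelling each visit by condition.

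**Cost:** two form fields, a few lines of text, and up to 3 extra forms per mixed visit. That is 6 to 12 per subject over 2 to 4 visits, or 72 to 144 for 12 completers if all visits have four mixed blocks. At an assumed 1 to 3 minutes each, the forms use 3 to 9 of the 15 break minutes in a visit. Repeated asking may raise reports of mild sensations, and attribution of headache or fatigue stays imperfect because these can carry over between blocks.

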The organization of the human visual system is an ideal model system suited for evaluation of the steerability of TI stimulation. The primary methodological advancement of TI is stimulation of deeper structures leaving superficial structures near the electrodes unaffected. The human primary visual system is organized "retinotopically", that is, with respect to the center of gaze. It is located within the calcarine sulcus, located in the occipital lobe at the posterior of the head. The most posterior part of the sulcus represents the center of gaze, and the most anterior part of the sulcus represents the periphery. Using this feature, we will examine if stimulation targeting the anterior calcarine sulcus induces a detectable visual change within the peripheral visual field, without impacting the center of gaze, located more superficially. Additional control sessions will evaluate the precision of TI steering.

Visual stimulation has historically been used as a preliminary investigation of non-invasive stimulation, in the study of transcranial magnetic stimulation (TMS) and transcranial electrical stimulation (tES). These sessions in healthy participants have shown acute effects of stimulation (e.g. brief phosphenes, transient scotomas) that are transient.

Clinical significance:

The importance of the problem we are tackling with TI stimulation is enormous, clinically speaking.

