All participants will have a baseline visual field assessment with a computerized visual field device (a Humphrey field analyzer – HFA) to be completed in the BIDMC ophthalmology department. This assessment will also be completed at the end of each TI visit. The assessment consists of the participant being positioned against a forehead and chinrest while being asked to maintain fixation on a central target and while providing responses when a light stimulus is noted. One eye will be assessed at a time. The testing takes under 10 minutes. If an abnormality is noted at baseline, the study ophthalmologist will review the results and will share the findings with the patient in real-time and will recommend follow-up with their primary care provider and/or will recommend that they follow-up with a specialist provider in ophthalmology. They will be excluded from the study if an abnormality is discovered at baseline. If a change is noted at the end of a testing session, a study MD will evaluate the participant to determine the need for additional follow-up. If there are any immediate concerns, the participant will be further evaluated by the study ophthalmologist who will provide recommendations for observation or follow-up.

Visual Discrimination and Disruption Testing

Participants will be asked to perform a visual discrimination task within the targeted region of visual space and within a control region prior to, concurrently, and following TI stimulation.

Adaptive thresholds will be computed for orientation discrimination and contrast discrimination using an algorithmic approach. Discrimination thresholds for stimulated and unstimulated regions will be assessed using a within-subjects design using a repeated-measures ANOVA. Subjects will be asked to fixate at different locations on a screen and press a button, for example, to indicate where they see a visual stimulus.

TI Stimulation

TI stimulation will be generated by our prototype device and applied to the head via standard, carbon

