electrode pads. Similar to other forms of tES, TI will be delivered using a low amplitude (4mA or lower) electric current via a minimum of two and a maximum of 24 scalp electrodes. We will use computer simulations to optimize the location of the electrodes to maximize the amplitude of the envelope modulation in the targeted area (calcarine cortex subregions) while minimizing its amplitude in the neighboring or overlying cortex. Electrodes will be fitted with fiducial markers for post-processing localization of the electrodes in MRI. TI stimulation will be applied for up to 10 min (with 5-10s ramping-up and ramping-down periods) with a difference frequency of 1-80Hz.

As compared to modern tES, these values are reduced in duration, frequency and intensity relative to tES guidelines ("up to 60 minutes", frequencies up to 10kHZ), but follow overall guidance for rampingup and ramping down periods (Antal et al 2017, Clin Neurophysiology).

Control conditions will include non-TI controls (i.e. stimulation at a single frequency equal to the difference frequency of TI stimulation, thus no envelope of stimulation). TI delivered at the carrier frequency only, or TI with alternative difference frequencies expected to be suboptimal. The carrier frequency, as well as the current amplitude, will be selected according to the animal data, scaled according to the computer models, and governed by safety guidelines and considerations.

B. Statistical Considerations

a. **Sample Size Justification:** This study aims to assess the feasibility, focality, and steerability of TI stimulation in humans. Pilot testing with 9 healthy participants demonstrated the feasibility and safety of this study, and 9 participants were sufficient to identify a neurophysiological effect upon BOLD signal.

We aim to complete at least 12 subjects, but up to 20 will be entered to allow for attrition.

b. **Data Analysis:** This study has a primary aim of assessing visual discrimination thresholds before, during and after TI stimulation. These values will be entered into a repeated measures ANOVA to assess the impact of TI stimulation, with the primary outcome being an interaction between TIME factors (before, during and after TI) and visual field location (stimulated with TI vs unstimulated). All analysis will be conducted in either SPSS or R.

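### The primary TIME x location test has no term for stimulation condition and no rule matching the control region to the target, so drift within a block that is unequal at the two locations could pass for a TI effect

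*Combined protocol and SAP*

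**What the plan says.** - **Order.** Section B3.A (Temporal Interference Sessions) gives each block three steps: "Baseline visual discrimination task to assess threshold", then "TI stimulation paired with the visual discrimination task and visual disturbance assessment (10 minutes", then "Repeat visual discrimination task". On quantity: "Each visit will consist of up to four, 10 minute blocks of stimulation paired with a visual discrimination task". There are 2 to 4 such visits.
- **Practice.** The Visit 1 list in B3.A includes perimetry and a fixation screen. It does not list the discrimination task. The MRI visit has button presses to mapping stimuli, but no threshold measurement is described.
- **Control region.** Under Visual Discrimination and Disruption Testing, the task is performed "within the targeted region of visual space and within a control region prior to, concurrently, and following TI stimulation". No rule on eccentricity, hemifield or baseline threshold follows. The background (B2, TI Validation with Visual Field Stimulation) asks whether stimulation "induces a detectable visual change within the peripheral visual field, without impacting the center of gaze, located more superficially".
- **Primary test.** B3.B (Data Analysis) enters thresholds into a repeated-measures ANOVA "with the primary outcome being an interaction between TIME factors (before, during and after TI) and visual field location (stimulated with TI vs unstimulated"). The threshold scale, raw or log, is not stated.
- **Control stimulation.** B3.A provides tACS, no-offset (carrier-only) and suboptimal-difference-frequency blocks. No rule sets their order, and condition is not a factor in the primary test.

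**The concern.** TIME is fully confounded with test order, so the location factor is the only protection the primary test has against practice and fatigue. That protection works when both locations drift by the same amount on the analysed scale. The plan secures this neither by matching the locations nor by fixing a scale. The blocks that could show drift without TI are planned, but the primary test does not use them. This interaction carries the focality claim, so a false positive would be read as selective modulation of the target.

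**Working it through.** The plan has no figure of its own to reproduce here: it gives no threshold SD, effect size, drift or significance level. Only the sample size (12 completers, up to 20 entered) comes from the documents. All other inputs are assumptions, shown over a range.

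**Mechanism.** Let B_T and B_C be the baseline thresholds at target and control, and m_t a proportional drift common to both (m = 1 before stimulation). With two locations, the TIME x location interaction is the change over time in the target-minus-control difference.

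- Raw scale: D_t = m_t x (B_T - B_C). This is constant only if B_T = B_C or m_t does not change.
- Log scale: ln(m_t B_T) - ln(m_t B_C) = ln(B_T / B_C). This is constant whatever m_t is.

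Example with B_T = 2, B_C = 1 and a 20% fall: D goes from 2 - 1 = 1 to 1.6 - 0.8 = 0.8. The raw interaction is -0.2 with no stimulation effect. On the log scale it is zero.

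**Simulation 1: proportional drift, unequal baselines.** One-way repeated-measures F test on the location difference at three times, Greenhouse-Geisser corrected, 5% level, n = 12, linear drift, between-subject SD 0.3 and within-cell SD 0.10 in ln threshold, true effect zero. False-positive rates on raw thresholds, with ranges covering repeat runs:

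| Total drift | Baselines 1:1 | 2:1 | 3:1 |
|---|---|---|---|
| 2% | about 4% | about 4% | about 4% |
| 5% | about 4% | 5 to 6% | 7 to 8% |
| 10% | about 4% | 12 to 13% | 20 to 21% |
| 20% | 3 to 4% | 43 to 45% | 75% |

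On log thresholds the rates stay at 4 to 5%.

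Sensitivity:
- SD 0.05, 10% drift, 2:1: 39 to 40%.
- SD 0.15, 10% drift, 2:1: 7%.
- n = 20, SD 0.10, 20% drift, 2:1: about 70%. Enrolling more people makes a bias easier to detect as an effect.

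**Simulation 2: drift that differs by location.** d is the extra linear drift at one location by the after measurement, in SDs of the before-to-after change in the location difference (5% level, 20,000 runs per case):

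| d | TIME x location, n = 12 | TIME x location, n = 20 | Condition x TIME x location, n = 12 |
|---|---|---|---|
| 0 | 4.7% | 5.0% | 4.9% |
| 0.25 | 10.4% | 14.4% | 5.0% |
| 0.5 | 28.0% | 47.4% | 5.1% |
| 1.0 | 83.5% | 97.7% | 4.7% |

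Logs do not remove this kind of drift. The comparison with no-offset blocks does, provided the drift is the same in both block types.

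**Effect of a new baseline in each block.** If practice occurs only in the first block and thresholds are averaged over blocks (2:1, 20% drift, SD 0.10), the rate falls from about 43% with one block to 11 to 14% with four, 9% with eight and 6% with sixteen. If drift recurs in every block, averaging works the other way: four blocks cut the SD from 0.10 to 0.10/√4 = 0.05 and leave the bias intact. At 10% drift and 2:1 that is the 39 to 40% above, against 12 to 13% for one block.

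**The case against.** The other side has a good case, and much of it stands.

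- A reader might infer that the control region is in fact unmatched, or that it is the center of gaze. The documents do not say so. The periphery-versus-center contrast is in the background section and is never named as the target/control pair of the ANOVA. Participants fixate at different screen positions and have individual retinotopic maps, so matching is possible. What stands is that no matching rule is given.
- A reader might also infer that any ordinary practice or fatigue produces the interaction. It does not. Common drift on the analysed scale cancels, which is the purpose of the location factor. The proportional mechanism needs clearly unequal baselines, appreciable drift within a block and raw-scale analysis, all together. At 5% drift or less and SD 0.10 the excess is slight.
- The absence of practice is inferred from silence. Visit 1 lists none but does not exclude familiarization.
- Each block takes a new baseline, which dilutes first-exposure practice. It does not dilute drift that recurs within every block, and visits of about 3 hours with up to four blocks make that plausible.
- The plan is not without controls: no-offset blocks follow the same three steps and could carry the same drift. But as written they do not enter the primary test, and their order is not set.
- An opposite-hemifield control location is not automatically unstimulated. The electrode optimization minimizes the envelope in neighboring or overlying cortex and does not name that region. If it were partly stimulated, the contrast would shrink.

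**Conclusion.** The point holds as a conditional weakness that is cheap to remove. The fixed order, the missing matching rule, the unstated scale and the absence of a condition term together allow a positive primary result with no TI effect. The documents do not show that this will happen. The size depends on inputs the plan does not give: from no material inflation (equal baselines, or about 2% drift at SD 0.10) to 43 to 75% false positives (20% drift in every measured block, 2:1 to 3:1 baselines, SD 0.10, n = 12). A noisier setting (SD 0.15, between-subject SD 0.25) still gives about 23% and 44% for a 20% fall at those ratios. The highest figures should not be read as expected error rates. The change should be made because this one interaction carries the focality conclusion.

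**What to change.** 1. State that thresholds are analysed as logarithms. This removes proportional drift common to both locations, at no cost.
2. Add a short practice run of the same task at both locations at Visit 1, alongside the fixation screen. This takes about 10 minutes and addresses first-exposure practice, not recurring fatigue.
3. Define the control region in advance from each participant's retinotopic map, matched to the target on eccentricity or baseline threshold and with low modelled envelope amplitude. The mirror location is one candidate if the field model shows it is unstimulated. Keep center of gaze as a separate control for the depth hypothesis. Trials are then shared over one more location.
4. Before attributing the interaction to TI, test condition (TI against no-offset) x TIME x location, with block order counterbalanced. This uses blocks already planned. The cost is precision: with independent block errors of equal variance, the contrast has variance σ² + σ² = 2σ², so its standard error is √2, about 1.4 times that of the two-way contrast. The sample size should be justified for that contrast.
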